Clinical Study Protocol

Drug Substance AZD9567
Study Code D6470C00003
Version 3

19 March 2019

**A Phase 2a, Randomised, Double-blind, Parallel Study to Assess
the Efficacy, Safety and Tolerability of AZD9567 compared to
Prednisolone 20 mg in patients with active Rheumatoid Arthritis
(RA)**

Sponsor: AstraZeneca AB, [name], Sweden

This Clinical Study Protocol has been subject to a peer review according to AstraZeneca Standard procedures. The Clinical Study Protocol is publicly registered and the results are disclosed and/or published according to the AstraZeneca Global Policy on Bioethics and in compliance with prevailing laws and regulations.

CLINICAL STUDY PROTOCOL SYNOPSIS

A Phase 2a, Randomised, Double-blind, Parallel Study to Assess the Efficacy, Safety and Tolerability of AZD9567 compared to Prednisolone 20 mg in patients with active Rheumatoid Arthritis (RA)

International Co-ordinating Investigator

PPD

Division Internal Medicine and Dermatology, Rheumatology & Clinical Immunology

University Medical Center Utrecht

[name]

[name]

The Netherlands

Study site(s) and number of subjects planned

This Phase 2a Proof of Principle study will be conducted in a maximum of 10 sites in 2-3 countries. Approximately 80-100 patients will be enrolled to achieve 40 randomised.

Study design

This is a Phase 2a, double-blind, double dummy, parallel arm study in patients with active rheumatoid arthritis (RA). It comprises 5 clinic visits and one telephone visit during approximately 5 weeks.

At Visit 1 (screening visit) patients will be consented and screened for eligibility.

At Visit 2, which can occur 1-6 days after Visit 1, pre-dose/baseline assessments will be made. Thereafter, patients will be randomised in the ratio 1:1 to take either 40 mg AZD9567 or 20 mg prednisolone for 14 days once daily. Since this study is double-blind and AZD9567 and prednisolone are different formulations (oral suspension and capsules respectively), all patients will have to take both formulations every day (active AZD9567 + placebo to prednisolone or placebo to AZD9567 + active prednisolone).

A telephone call on study Day 5 to check on patient well-being will be termed Visit 3.

Clinic Visit 4 will occur 7 days into the treatment and Visit 5 will be the end of treatment visit occurring approximately 14 days after Visit 2.

A follow-up visit, Visit 6, will be performed approximately 14 days after last IMP administration on Visit 5, in order to ensure the safety and well-being of patients.

Objectives

Primary Objective:	Outcome Measure:
To assess the efficacy of AZD9567, 40 mg, compared to prednisolone 20 mg in patients with active rheumatoid arthritis in spite of stable treatment with conventional and/or s.c./i.v. biological DMARDs	Change from baseline in 28 joint Disease Activity Score using CRP (DAS 28 - CRP)

Secondary Objective:	Outcome Measure:
To further assess the efficacy of AZD9567, 40 mg, compared to prednisolone 20 mg in patients with active rheumatoid arthritis in spite of stable treatment with conventional and/or s.c./i.v. biological DMARDs	Proportion of subjects reaching ACR (American College of Rheumatology) 20, 50 and 70 responses Change from baseline in Swollen Joint Count 66 (SJC 66) Change from baseline in Tender Joint Count 68 (TJC 68) Change from baseline in individual components of DAS28 and ACR response criteria (number of swollen and tender joints, patients assessments of global disease activity, pain, physician's global assessment of disease activity, and CRP)
To evaluate the pharmacokinetic profile of AZD9567 in patients with active rheumatoid arthritis in spite of stable treatment with conventional and/or s.c./i.v. biological DMARDs	E g but not limited to plasma AUC ₍₀₋₂₄₎ , AUC _(0-last) , C _{max} and t _{max} .

Safety Objective:	Outcome Measure:
To assess the safety and tolerability of AZD9567 in patients with active rheumatoid arthritis in spite of stable treatment with conventional and/or s.c./i.v. biological DMARDs	Adverse events, vital signs, ECG and laboratory parameters (haematology, clinical chemistry and urine)

Exploratory Objective:	Outcome Measure:
To evaluate the pharmacokinetic profile of prednisolone in patients with active rheumatoid arthritis in spite of stable treatment with conventional and/or s.c./i.v. biological DMARDs	E g but not limited to plasma AUC ₍₀₋₂₄₎ , AUC _(0-last) , C _{max} and t _{max} .

Exploratory Objective:	Outcome Measure:

To assess the responses to AZD9567 of relevant biomarkers. Whole blood and serum/plasma will be collected to enable relevant analyses such as, but not limited to, effects on bone, metabolism and HPA axis.
 
Exploratory variables will be reported in a separate biomarker report and will not be included in the clinical study report (CSR), unless something clinically important is observed.
	Exploratory blood biomarkers (e.g. LPS stimulated TNF _α , cortisol and other possible exploratory markers including RNA)

To obtain optional blood samples for future pharmacogenetic (PGx) research aiming to identify/explore pharmacodynamic biomarkers or genetic variations that may affect the efficacy, pharmacodynamics, safety and tolerability profile related to AZD9567 treatment.
 
Data from the PGx research will not be included in the CSR.
	DNA from whole blood

Target subject population

The study population will comprise adult patients with active rheumatoid arthritis in spite of stable treatment with conventional Disease-modifying anti-rheumatic drugs.

Duration of treatment

The total duration of the study for each patient is approximately 5 weeks, which includes a 2 week treatment period and up to 2 week follow up period. The screening period can be up to one week or as short as 1-2 days.

Investigational product, dosage and mode of administration

AZD 9567 is a non-steroidal selective glucocorticoid receptor modulator. In the study the aim is to investigate the safety, efficacy and tolerability of AZD9567 compared to prednisolone in patients with active Rheumatoid Arthritis.

The drug substance is presented as a drug powder and formulated as a suspension for oral administration, using standard excipients. A placebo formulation, an oral suspension, using inactive standard excipients is included in the study. A comparator product, prednisolone capsules and placebo for prednisolone capsules, will also be used. The dose of AZD9567 will be 40 mg once daily (OD) and the dose of prednisolone is 20 mg OD.

Statistical methods

The main objective of this study is to demonstrate that the efficacy of AZD9567 is equivalent to the efficacy of prednisolone 20 mg, where the efficacy endpoint used is change from baseline (CFBL) in DAS28. More precisely, we will use the difference in DAS28 units, $X_T - X_p$, between, X_T , the average CFBL of the chosen dose of AZD9567 and, X_p , the mean CFBL of prednisolone 20 mg to estimate the average difference in DAS28 between the two arms. This difference will be calculated using a mixed model.

The primary analysis population for efficacy will be the intention to treat (ITT) population. This will include all patients who were randomised and received at least one dose of study medication. Patients will thus be analyzed according to the treatment to which they were intended to be randomised to.

TABLE OF CONTENTS

1.	INTRODUCTION	15
1.1	Background and rationale for conducting this study	15
1.2	Rationale for study design, doses and control groups	15
1.3	Benefit/risk and ethical assessment	16
1.4	Study Design	17
1.5	Study governance and oversight (Not Applicable).....	19
2.	STUDY OBJECTIVES.....	19
2.1	Primary objective.....	19
2.2	Secondary objectives	19
2.3	Safety objectives.....	19
2.4	Exploratory objectives	20
3.	SUBJECT SELECTION, ENROLMENT, RANDOMISATION, RESTRICTIONS, DISCONTINUATION AND WITHDRAWAL	20
3.1	Inclusion criteria	20
3.1.1	Acceptable birth control methods.....	21
3.2	Exclusion criteria	22
3.3	Subject enrolment and randomisation.....	23
3.4	Procedures for handling incorrectly enrolled or randomised subjects.....	23
3.5	Methods for assigning treatment groups.....	23
3.6	Methods for ensuring blinding	24
3.7	Methods for unblinding.....	24
3.8	Restrictions.....	25
3.9	Discontinuation of investigational product	25
3.9.1	Procedures for discontinuation of a subject from investigational product	25
3.10	Criteria for withdrawal.....	26
3.10.1	Screen failures	26
3.10.2	Rescreening	26
3.10.3	Withdrawal of the informed consent	26
3.11	Discontinuation of the study	26
4.	STUDY PLAN AND TIMING OF PROCEDURES	28
4.1	Screening/Enrolment period.....	30
4.2	Treatment period.....	30
4.3	Follow-up period	30
5.	STUDY ASSESSMENTS.....	30
5.1	Efficacy assessments.....	31
5.1.1	DAS 28.....	31
5.1.2	Swollen and Tender Joint Count 66/68.....	31

5.2	Safety assessments.....	32
5.2.1	Laboratory safety assessments	32
5.2.2	Physical examination	34
5.2.3	ECG	34
5.2.3.1	Resting 12-lead ECG	34
5.2.4	Vital signs.....	34
5.2.4.1	Pulse and blood pressure.....	34

IMP	Investigational Medicinal Product
IxRS (IWRS/IVRS)	Interactive Web/Voice Response System
ITT	Intention to treat
LIMS	Laboratory Information Management System
LPS	Lipopolysaccharide (used as challenging agent in e g blood cell biomarker analyses)
LSLV	Last Subject Last Visit
OAE	Other Significant Adverse Event
OC	Overencapsulated

Abbreviation or special term	Explanation
Gx	Genetic research
OGTT	Oral glucose tolerance test
PI	Principal Investigator
PK	Pharmacokinetics
PRO	Patient Reported Outcome
SAE	Serious Adverse Event
SAP	Statistical Analysis Plan
SGRM	Selective glucocorticoid receptor modulator
SJC66/68	Swollen Joint Count, assessing 66 or 68 joint
TJC	Tender Joint Count
T _{max}	Time point of the maximal plasma concentration of a drug
WBDC	Web Based Data Capture
WOCBP	Women of Child Bearing Potential

1. INTRODUCTION

1.1 Background and rationale for conducting this study

Rheumatoid arthritis (RA) is a chronic systemic inflammatory disease that is associated with significant morbidity and mortality. The disease is characterized by inflammation of the synovial joints that can result in pain, swelling, and joint damage with secondary deformity and progressive disability. Worldwide, the prevalence of RA is estimated to be between 0.6% and 1.1% with variations across geographical regions (Pincus et al, 1987, Harris, 1997, Symmons, 2002). Uncontrolled active RA causes joint damage, disability and decreased quality of life, comorbidities including cardiovascular disease and osteoporosis, and reduced life expectancy (Wong et al, 2001, Pincus et al, 1989, Harris, 1997).

Oral glucocorticoids (GC), such as prednisolone, have been used for the treatment of signs and symptoms of RA since before the 1950's (Hench et al, 1949) and remain an important component of the treatment paradigm for both early and established RA [ACR guidelines 2015]. GC modulate the activities of a variety of inflammatory cells and mediators in the synovium of RA patients contributing its therapeutic efficacy (Gerlag et al, 2004). The challenge of GC treatment for the clinicians has been the safety/tolerability of GC especially after long-term use particularly with respect to effects on osteoporosis (Siu et al, 2015), risk of diabetes (Gulliford et al, 2006) cardiovascular disease (del Rincon et al, 2014) and mortality (del Rincon et al, 2014).

AZD9567 is a non-steroidal selective glucocorticoid receptor modulator (SGRM) that has potential to be used as an oral treatment for RA. Pre-clinical studies have been able to show significant anti-inflammatory effect with a differentiation between desired efficacy and the unwanted effects (eg, glucose metabolism, bone effects and mineralocorticoid effect) in nonclinical models and systems. AZD9567 has also been safe and well tolerated thus far in clinical studies of healthy volunteers. Therefore, there is strong pre-clinical evidence supporting the use of an oral SGRM in the therapy of RA.

This is a first-in-patients, Phase 2a, randomised, double-blinded, parallel arm study designed to assess the efficacy of one dose level of AZD9567 compared to prednisolone 20mg once daily in rheumatoid arthritis patients as evaluated by change from baseline of DAS28-CRP. This study will also evaluate the safety, tolerability and PK of AZD9567.

1.2 Rationale for study design, doses and control groups

This is a Phase 2a, randomised, double-blind, parallel arm study to assess the efficacy, safety and tolerability of 40 mg AZD9567 compared to prednisolone 20 mg in patients with active RA. According to the American College of Rheumatology Guidelines, short-term glucocorticoid treatment is indicated to control disease in RA patients with moderate to high disease activity. The current study randomizes eligible patients with established RA and

moderate to high disease activity as defined by ACR Guidelines (DAS28>3.2) to prednisolone 20 mg or AZD9567 40 mg for 14 days.

Prednisolone 20 mg is chosen as a moderate dose of prednisolone that falls within the ACR recommendations for treatment of active disease as moderate doses have been shown to be as effective as higher doses in active early RA ([ter Wee et al, 2015](#)). A two weeks duration of therapy was chosen on the basis that prior study has suggested that this duration can significantly impact disease activity as measured by DAS28 score ([Gerlag et al, 2004](#)).

A dose AZD9567 of 40 mg has been selected based on review of available safety, PK, and PD data from the first studies in humans in which AZD9567 was administered to healthy volunteers as single doses 2, 10, 20, 40, 80, 100, 125 and 155 mg (D6470C00001) and, in a multiple dose setting, once daily for 5 days using 10, 20, 40 and 80 mg. (D6470C00002). AZD9567 was well tolerated in all studied dose levels.

The selected AZD9567 dose 40 mg showed effects on inflammatory activity (reduced lipopolysaccharide (LPS) stimulated TNF_α response) and on the HPA axis (plasma cortisol reduction) similar to what was observed for 20 mg prednisolone.

Although the selected comparator dose of 20 mg prednisolone is known to be efficacious in RA and considered safe and tolerable for 14 days administration, it also has significant effect on glucose homeostasis. The 40 mg dose of AZD9567 showed a significantly better side effect profile with respect to glucose levels after an oral glucose tolerance test (OGTT) compared to prednisolone 20 mg in the ongoing MAD study (D6470C00002).

1.3 Benefit/risk and ethical assessment

AZD9567 is an oral, non-steroidal, potent and selective glucocorticoid receptor modulator (SGRM) under development for the treatment of rheumatoid arthritis. Experience has been gathered from non-clinical safety pharmacology, toxicology studies, previous clinical experience with GR agonists and preliminary data from the first in man single ascending dose study (D6470C00001) and the ongoing multiple ascending dose study (D6470C0002).

In preclinical testing AZD9567 displays features consistent with a potent GR agonist and expected findings in humans will be monitorable and reversible. In clinical studies of AZD9567, single doses of AZD9567 up to 155 mg, and multiple doses of AZD9567 up to 80 mg have been well tolerated in healthy volunteers. Based upon this experience, it is expected that the dose of 40 mg will be well tolerated in RA patients.

Potential adverse effects are discussed in the Investigator's Brochures (Section [6.1](#)). They include potential effects on glucose and lipid metabolism, bone metabolism, and inflammation. The occurrence of any AE, abnormality in laboratory variables or any other safety variables will be closely monitored and evaluated on an ongoing basis during the

clinical studies. Potential benefit for patients taking part in the current study include improvement of their symptoms and decrease in RA disease activity. Using the described measures to avoid exposing the subjects participating in studies to unacceptable risks, it is thus concluded that the potential benefits compared to risks of evaluating AZD9567 justify its further evaluation in this Phase 2a Study.

1.4 Study Design

This is a Phase 2a, double-blind, double dummy, parallel study in patients with active rheumatoid arthritis (RA) in spite of stable treatment with conventional disease-modifying anti-rheumatic drugs (DMARDs). A total of 40 patients will be randomised in the study.

At Visit 1 (screening visit) eligible patients will be identified. Patients will be asked to provide informed consent after which screening assessments will be performed.

[figure not shown]
At Visit 2, patients will be randomised in a ratio 1:1 to take either AZD9567 40 mg or prednisolone 20 mg for 14 days once daily. Since this study is double-blind and AZD9567 and prednisolone are different formulations (oral suspension and capsules respectively), all patients will have to take both formulations every day (active AZD9567 + placebo to prednisolone or placebo to AZD9567 + active prednisolone). A telephone call to check patient well-being will be termed Visit 3. Visit 4 will occur approximately 7 days after Visit 2, and Visit 5, which is the end-of-treatment visit, will occur approximately 14 days after Visit 2.

A follow-up visit (Visit 6) will be performed approximately 14 days after last IMP administration (at Visit 5) in order to ensure the safety and well-being of patients.

For more information regarding the visits and time windows please refer to the study flowchart, [Figure 1](#).

For details of the study assessments, please see [Table 1](#) in Section 4.

Figure 1 Study flow chart

1.5 Study governance and oversight (Not Applicable)

2. STUDY OBJECTIVES

2.1 Primary objective

Primary Objective:	Outcome Measure:
To assess the efficacy of AZD9567, 40 mg, compared to prednisolone 20 mg in patients with active rheumatoid arthritis in spite of stable treatment with conventional and/or s.c/i.v. biological DMARDs	Change from baseline in 28 joint Disease Activity Score using CRP (DAS 28 - CRP)

2.2 Secondary objectives

Secondary Objective:	Outcome Measure :
To further assess the efficacy of AZD9567, 40 mg, compared to prednisolone 20 mg in patients with active rheumatoid arthritis in spite of stable treatment with conventional and/or s.c/i.v. biological DMARDs	Proportion of subjects reaching ACR (American College of Rheumatology) 20, 50 and 70 responses Change from baseline in Swollen Joint Count 66 (SJC 66) Change from baseline in Tender Joint Count 68 (TJC 68) Change from baseline in individual components of DAS28 and ACR response criteria (number of swollen and tender joints, patients assessments of global disease activity, pain, physician's global assessment of disease activity, and CRP)
To evaluate the pharmacokinetic profile of AZD9567 in patients with active rheumatoid arthritis in spite of stable treatment with conventional and/or s.c/i.v. biological DMARDs	E g but not limited to plasma AUC ₍₀₋₂₄₎ , AUC _(0-last) , C _{max} and t _{max} .

2.3 Safety objectives

Safety Objective:	Outcome Measure :
To assess the safety and tolerability of AZD9567 in patients with active rheumatoid arthritis in spite of stable treatment with conventional and/or s.c/i.v. biological DMARDs	Adverse events, vital signs, ECG and laboratory parameters (haematology, clinical chemistry and urine)

2.4 Exploratory objectives

Exploratory Objective:	Outcome Measure :
To evaluate the pharmacokinetic profile of prednisolone in patients with active rheumatoid arthritis in spite of stable treatment with conventional and/or s.c./i.v. biological DMARDs	E g but not limited to plasma AUC ₍₀₋₂₄₎ , AUC _(0-last) , C _{max} and t _{max} .
To assess the responses to AZD9567 of relevant biomarkers. Whole blood and serum/plasma will be collected to enable relevant analyses such as, but not limited to, effects on bone, metabolism and HPA axis. Exploratory variables will be reported in a separate biomarker report and will not be included in the clinical study report (CSR), unless something clinically important is observed.	Exploratory blood biomarkers (e g LPS stimulated TNF _α , cortisol and other possible exploratory markers including RNA)
To obtain optional blood samples for future pharmacogenetic (PGx) research aiming to identify/explore pharmacodynamic biomarkers or genetic variations that may affect the efficacy, pharmacodynamics, safety and tolerability profile related to AZD9567 treatment. Data from the PGx research will not be included in the CSR.	DNA from whole blood

3. SUBJECT SELECTION, ENROLMENT, RANDOMISATION, RESTRICTIONS, DISCONTINUATION AND WITHDRAWAL

Each subject should meet all of the inclusion criteria and none of the exclusion criteria for this study. Under no circumstances can there be exceptions to this rule.

3.1 Inclusion criteria

For inclusion in the study subjects should fulfil the following criteria:

- 1 Provision of informed consent prior to any study specific procedures
- 2 Male and female patients aged 18 through 80 years at screening
- 3 Established RA diagnosis according to the 2010 American College of Rheumatology (ACR)/EULAR classification or the 1987 criteria
- 4 Active RA (DAS28-CRP score ≥ 3.2) with at least 3 swollen joints and 3 tender joints using the DAS28 joint count

- 5 Patients must have been on stable dosing of conventional and/or s.c./i.v biological DMARDs for the last 8 weeks prior to Visit 1
- 6 CRP levels >5mg/L at screening if seronegative for RF and anti-CCP Ab, or >2mg/L if seropositive for either marker
- 7 BMI between 18 and 35 (inclusive)
- 8 Negative pregnancy test (serum) for female subjects of childbearing potential.
- 9 Female subjects must be 1 year post-menopausal, surgically sterile, or using an acceptable method of contraception (defined as a barrier method in conjunction with a spermicide) for the duration of the study, for details refer to Section 3.1.1
- 10 Male subjects must be surgically sterile or using an acceptable method of contraception (defined as barrier methods in conjunction with spermicides) for the duration of the study (from the time they sign consent) and for 1 month after the last dose of IMP to prevent pregnancy in a partner.
- 11 Subjects who are blood donors should not donate blood during the study and for 3 months following their last dose of IMP.

For inclusion in this genetic research, subjects must fulfil all of the inclusion criteria described above **and**:

- 12 Provide informed consent for the genetic sampling and analyses.

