3.1.1 Acceptable birth control methods

Female patients are not pregnant and do not plan to become pregnant during the study, are not lactating, or are of non-childbearing potential. Females of childbearing potential must provide a negative serum pregnancy test at screening, have a date of last menstruation consistent with non-pregnancy, negative urine pregnancy tests at the follow-up visit, and must be using at least one highly effective method of contraception.

Women not of childbearing potential are defined as women who are either permanently sterilized (hysterectomy, bilateral oophorectomy, or bilateral salpingectomy, but excludes bilateral tubal occlusion), or who are postmenopausal.

Women will be considered postmenopausal if they have been amenorrhoeic for 12 months or more following cessation of exogenous hormonal treatment prior to the planned date of randomisation without an alternative medical cause and have follicle stimulating hormone (FSH) levels in the postmenopausal range.

Acceptable methods of contraception are tubal occlusion, intrauterine device (provided coils are copper-banded), levonorgestrel intrauterine system (e.g., MirenaTM), medroxyprogesterone injections (e.g., Depo-ProveraTM), etonogestrel implants (e.g., ImplanonTM, NorplanTM), normal and low dose combined oral pills, norelgestromin/ethynodiol transdermal system,

intravaginal device (e.g., ethinylestradiol and etonogestrel), desogestrel (e.g., CerazetteTM), total sexual abstinence and vasectomized sexual partner (with participant assurance that partner received post-vasectomy confirmation of azoospermia). Women should have been stable on their chosen method of contraception for a minimum of 3 months before entering the trial and should continue with contraception for 1 month after the last dose of IMP. In addition to the acceptable method of contraception (except for the practice of total sexual abstinence), condom should be used by male partner for sexual intercourse from randomisation and for 1 month after the last dose of IMP to prevent pregnancy.

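### Inclusion criterion 9 defines acceptable female contraception as barrier plus spermicide, which is not among the methods in Section 3.1.1, the section it cites

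*Protocol*

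**What the plan says.** Protocol Section 3.1, criterion 9, gives a woman three ways to qualify: post-menopausal for a year, surgically sterile, or using acceptable contraception. The third is "defined as a barrier method in conjunction with a spermicide", followed by "for details refer to Section 3.1.1".

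Section 3.1.1 says that a woman of childbearing potential "must be using at least one highly effective method of contraception". Its list begins "Acceptable methods of contraception are tubal occlusion, intrauterine device (provided coils are copper-banded" and continues through hormonal methods to abstinence and a vasectomised partner. The condom comes afterwards, as an extra: "In addition to the acceptable method of contraception (except for the practice of total sexual abstinence), condom should be used by male partner". The section also says that women "should continue with contraception for 1 month after the last dose of IMP".

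Section 3.1.1 counts hysterectomy, bilateral oophorectomy and bilateral salpingectomy as permanent sterilisation and expressly leaves out bilateral tubal occlusion. Criterion 9 does not define surgical sterility.

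Section 3, introducing the eligibility criteria, states: "Under no circumstances can there be exceptions to this rule".

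**The concern.** One term has two definitions, and the second sits in the section that is meant to explain the first. Criterion 9 says that its method is *defined as* barrier plus spermicide; it does not offer this as an example. A site that works from the wording of criterion 9 could randomise a woman who uses only that method. A site that follows the cross-reference would have to exclude her. The no-exceptions clause leaves neither site any stated discretion.

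The error that matters runs in the less protective direction: a woman of childbearing potential could be dosed without the contraception that Section 3.1.1 makes mandatory. Section 1.1 describes the study as the first in patients, and Section 4.2 notes that 5 days is the longest regimen given so far, against 14 days here. The same woman could also be recorded as eligible or as an eligibility deviation, depending on which text is applied. Failure to meet eligibility criteria is one of the categories in SAP Section 2.2.1 for identifying important protocol deviations.

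**Working it through.** No formula applies. The check sets the two texts side by side and counts.

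**Methods listed in Section 3.1.1**

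1. Tubal occlusion
2. Copper-banded intrauterine device
3. Levonorgestrel intrauterine system
4. Medroxyprogesterone injection
5. Etonogestrel implant
6. Combined oral pill (normal and low dose counted as one)
7. Transdermal system
8. Intravaginal device
9. Desogestrel
10. Total sexual abstinence
11. Vasectomised partner

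Total: 11. Number that are barrier plus spermicide: 0. Spermicide is not mentioned anywhere in the section.

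**Can the condom sentence reconcile the texts?** No. Section 3.1.1 adds the condom to an acceptable method, so the condom is not itself one of them, and no spermicide goes with it.

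**Can both texts be required together?** Only by adding a barrier with spermicide to every listed method, including abstinence, which Section 3.1.1 accepts alone and exempts from the condom. Nothing in the protocol tells sites to do this.

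**The case that separates the two rules**

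| Woman of childbearing potential using | Criterion 9 as worded | Section 3.1.1 |
|---|---|---|
| Barrier plus spermicide only | Met | Not met |

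**Which text is out of line?** Section 3.8 restricts CYP3A4 inducers in women who use hormonal contraceptives. It therefore expects such women in the study, as Section 3.1.1 does. The parenthesis in criterion 9 stands alone.

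**A related ambiguity: tubal occlusion.** Section 3.1.1 is consistent with itself here. It does not count tubal occlusion as permanent sterilisation, but accepts it as contraception with a partner's condom. Because criterion 9 leaves surgical sterility undefined, a site could admit the same woman as sterile and not ask for the condom.

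**Upper limit on patients.** SAP Section 1.3 gives an agreed 10 per group, so 2 × 10 = 20 patients of both sexes. The documents do not say how many are women of childbearing potential, or how many of those rely on barrier plus spermicide alone.

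**The case against.** The strongest defence is the cross-reference. Criterion 9 points to Section 3.1.1 in the same sentence, and a site that reads both has a workable, stricter rule: a listed method plus a partner's condom. Harm requires a site to stop at the parenthesis. Treatment lasts 14 days, Table 1 schedules serum pregnancy tests at screening and Visit 6, and Section 6.6.1 requires immediate discontinuation if a patient becomes pregnant. SAP Section 6 also reports an agreement to close recruitment early, which may remove any benefit for enrolment.

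Most of this stands, and it limits the practical weight. It does not remove the contradiction: a section cited for details should elaborate a definition, and this one replaces it. Pregnancy tests detect a pregnancy; they do not prevent one.

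Two stronger readings are tempting, and the documents do not support them.

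- A reader might infer that women may stop contraception at Visit 6, because criterion 9 mentions only the study period while criterion 10 asks men to continue "for 1 month after the last dose of IMP to prevent pregnancy in a partner". Section 3.1.1 already gives women the same extra month, and criterion 9 refers to it.
- A reader might infer that pill or device users would be turned away for lack of spermicide. That follows from the literal wording, but Section 3.8 plainly expects hormonal users, so it is not a realistic reading.

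**Conclusion.** Wrong as written: an internal inconsistency in a safety-related eligibility rule. None of the 11 methods in Section 3.1.1 matches the definition in criterion 9, and a woman using only barrier plus spermicide passes one text and fails the other. It should be corrected.

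The practical effect is small. It depends on a site applying the parenthesis without the cross-reference, and on such a woman being screened; the documents allow no estimate of either. The judgement that Section 3.1.1 is the intended rule rests on its mandatory wording and on Section 3.8.

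A reader might go further and infer that the trial's results are at risk. They are not: sample size, power and the primary analysis do not depend on this text. SAP Section 2.1.5 removes patients from the per-protocol set only for important deviations judged to affect the primary endpoint analysis, or for not completing the study, so a contraception deviation would not by itself lead to exclusion.

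**What to change.** In criterion 9, delete the parenthesis and write: *using an acceptable, highly effective method of contraception as listed in Section 3.1.1, with partner condom use as described there, throughout the study and until 1 month after the final IMP dose*. The added month only aligns criterion 9 with Section 3.1.1. In the same criterion, tie surgical sterility to Section 3.1.1's definition of permanent sterilisation, which leaves out bilateral tubal occlusion.

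If recruitment has closed, issue a clarification that Section 3.1.1 governs. Any woman enrolled on barrier plus spermicide alone should go through the existing route: Section 3.4 (inform the study physician at once, discuss whether treatment continues, document the decision) and the protocol-deviation assessment in SAP Section 2.2.

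The cost is a sentence in an amendment or a short clarification letter. No new procedure is needed, because Section 3.1.1 already contains the rule.
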